2. STUDY SYNOPSIS

Sponsor:	Retrotope, Inc. [name]
Title:	A Randomized, Double-Blind, Controlled, Phase 2/3 Study to Assess Efficacy, Long Term Safety and Tolerability of RT001 in Subjects with Friedreich's Ataxia
Protocol No:	RT001-006
Study Drugs:	Active : RT001, 960 mg soft gelatin capsules (9-cis, 12-cis-11,11-D ₂ -linoleic acid ethyl ester [deuterated ethyl linoleate, or D ₂ -LA])
	Placebo: Soft gelatin capsule of USP safflower oil (Placebo or H ₂ -LA)
Study Population:	Friedreich's ataxia (FRDA) patients who meet all entry criteria.
Number of Subjects	The planned enrollment is 60 subjects randomized 1:1 (active: placebo). Randomization will be stratified by Friedreich Ataxia Rating Scale (FARS) Neurological score: ≤45 and >45 Enrollment of patients with age > 25 will be capped at 25 % of the total enrollment
Dosing Schedule	Subjects will receive the content of nine capsules daily (8.64 g total dose) given as 3 capsules three times a day (TID) with meals for the first month of treatment. After this initial loading period, the dose will be reduced to six capsules daily (5.76 g total dose) given as 3 capsules with breakfast, and 3 capsules with dinner for the remainder of the trial, while on study drug. If a subject is unable to tolerate study drug because of adverse events during the initial loading period, the dose may be reduced to six capsules daily (5.76 g total dose) given as 3 capsules with breakfast, and 3 capsules with dinner. If a subject is unable to tolerate study drug because of adverse events after the dose reduction to six capsules daily (5.76 g total dose), the dose may be spread over three meals (2 capsules at breakfast, 2 capsules with lunch, and 2 capsules with dinner). If the subject is still unable to tolerate study drug after spreading it over three meals, the total dose may be reduced by 1-2 capsules/day, preferably by reducing the dose for a meal from 2 to 1 capsule(s) as needed. After 2 weeks of taking a dose of less
	than 6 caps/day, the subject should try to increase the dose to 6 capsules/day given as 2 capsules TID given with meals. If 6 caps/day is not tolerable, the subject can take the drug at the dose of less than 6 caps/day that was tolerable.
Route of Administration:	Oral
Study Centers:	up to 10 study centers
Phase of Development	Phase 2/3

Objectives

Primary endpoints:

1. To demonstrate the efficacy of RT001 compared to placebo on the change of MVO2 in patients with FA through change from baseline to 11 months

Key secondary endpoint:

1. To demonstrate the efficacy of RT001 compared to placebo on an overall performance score based on a Global Statistical Test (GST) change from baseline to 11 months. The GST will be a combination of three endpoints (timed 1 minute walk test [T1MW], peak workload, and maximum rate of oxygen consumption [MVO2]).

Secondary endpoints:

- 1. To demonstrate the efficacy of RT001 compared to placebo on T1MW with change from baseline to 11 months
- 2. To demonstrate the efficacy of RT001 compared to placebo on the change of peak workload measured by CPET through change from baseline to 11 months.

Exploratory endpoints:

To demonstrate the efficacy of RT001 on change from baseline at 11 months in clinical symptoms as measured by:

- 1. Modified Friedreich's Ataxia Scale (mFARS)
- 2. Fatigue Symptom Scale (items 2. 4. 7.9 of the total fatigue scale)
- 3. Clinician-rated Clinical Global Impression of Change (CGI-C)
- 4. Activities of daily living (ADL) elements of fatigue scale (items 5,6, 8, 10, and 11)
- 5. Patient Global Impression of Change (PGI-C)
- To evaluate the effects of RT001 on Visual Analogue Scale [VAS]
- To evaluate the effects of RT001 on speech measurements and Speech Assessment questionnaire
- To evaluate the effect of RT001 on a timed 25-feet walk (T25FW)
- To evaluate the effects of RT001 on the neurological examination of the Friedreich Ataxia Rating Scale (FARS-Neuro)
- To evaluate the effects of RT001 on the activities of daily living of the Friedreich Ataxia Rating Scale (FARS-ADL)
- To evaluate the effects of RT001 on SF-36
- To evaluate the effects of RT001 on the Neuro-QoL scales (Upper Extremity Function and Lower Extremity Function)
- To evaluate the effects of RT001 on the frequency of falls as reported in a fall diary and subject's fear of falling
- To evaluate the effects of RT001 on the Patient Global Impression of Change (PGI-C) Scale
- To evaluate the effects of RT001 on efficacy assessments after 4 months of treatment
- To evaluate the effects of RT001 on efficacy assessments after 8 months of treatment
- To evaluate the effects of RT001 on ejection fraction as reported in the Echocardiogram
- To evaluate the effects of RT001 on hypertrophy as reported in the Echocardiogram

Optional PK Profile Sub-Study Objective:

	The objective of the study is to evaluate the pharmacokinetic (PK) profile of RT001 at steady state. Optional PK Washout Sub-Study Objective: The objective of the study is to evaluate the washout blood levels of RT001 after treatment in RT001-006 is completed.
Study Methodology	This is a randomized, double-blind, placebo-controlled study to evaluate the efficacy, safety, tolerability, in subjects with FRDA following the oral administration of study drug (active or placebo capsules). Subjects will self-administer the study drug orally with meals. While on study drug, subjects are recommended to avoid eating foods high in PUFAs. Subjects will keep food journals from screening through the completion of month 1 on study drug. After month 1, subjects will keep 2-week food journals prior to the next scheduled onsite visit. Subjects (or parents/caregivers, as applicable) will have an initial call and as needed with the diet coach to discuss food journal completion requirements.
	CPET and the T1MW/T25FW should be separated in time to allow the subject to recover sufficiently before doing the next test. CPET should occur in the morning after fasting for a minimum of 2 hours (if the subject has had a meal/snack), with neither caffeine nor nicotine for at least 12 hours before testing. All tests should be done at approximately the same time and order each day.
Study Duration	Participation is anticipated to require 13 months. • Screening: Up to 30 days from start of treatment • Treatment Period: treatment for a 12-month period For patients who consent to the Optional Washout Sub-Study Objective, the study duration will be 19 months.
Study Design	The planned enrollment is 60 subjects randomized 1:1 active: placebo. There are two optional PK sub-studies. Subjects will have the opportunity to consent to these studies at the Day 330 visit or at the time of the first draw. **Randomized, Blinded Period* Informed consent Profile Sub-Study
Safety Assessments	Safety assessments include physical and neurologic examinations, vital signs, 12-lead electrocardiogram (ECG) tracing, and clinical laboratory tests (hematology, clinical chemistry, lipid profile, coagulation, and urinalysis) to identify adverse events (AEs). Adverse events will be evaluated for incidence, severity, and relationship to study drug. Any AE ongoing at the End of Treatment (EOT) phone call will be followed to conclusion or until stabilized.

PK/Biomarker Analysis

Bioanalytical measurements will be performed to determine the concentration of D2-LA, deuterated arachidonic acid (D2-ARA), H2-LA and nondeuterated arachidonic acid (H2-ARA) in plasma, and D2-LA, D2-ARA H2-LA, and H2-ARA in red blood cells.

Blood samples will be collected for the plasma measurements as follows:

Month 4 (Day 120 ± 30 days): Pre-dose (prior to breakfast) Month 8 (Day 240 ± 30 days): Pre-dose (prior to breakfast) Month 11 (Day 330 ± 30 days): Pre-dose (prior to breakfast)

Blood samples for the assessments in red blood cells will be collected as follows:

Month 4 (Day 120 ± 30 days): Pre-dose (prior to breakfast) Month 8 (Day 240 ± 30 days): Pre-dose (prior to breakfast) Month 11 (Day 330 ± 30 days): Pre-dose (prior to breakfast)

Additional blood samples will be collected and stored for future biomarker analysis as follows:

Day 1: Pre-dose (prior to breakfast)

Month 4 (Day 120 ± 30 days): Pre-dose (prior to breakfast) Month 8 (Day 240 ± 30 days): Pre-dose (prior to breakfast) Month 11 (Day 330 ± 30 days): Pre-dose (prior to breakfast)

Two additional optional PK sub-studies are offered. The first study is a 24hr PK Profile at steady state that will occur immediately before or after the Day 330 visit. Blood samples for this study will be collected as follows:

Day 1: Hour -1.0 to -0.5 (pre-breakfast, pre-dose), $0.5 (\pm 5 \text{ min})$, $1 (\pm 5 \text{ min})$, $2 (\pm 10 \text{ min})$, $4 (\pm 15 \text{ min})$ (pre-lunch), $8 (\pm 15 \text{ min})$ (pre-dinner), and $12 (\pm 60 \text{ min})$

Day 2: 24 hours following dosing on Day 1 (± 60 min; pre-breakfast, pre-dose)

The second optional sub-study is a 6-month study to evaluate the washout blood levels of RT001 after treatment in RT001-006 is completed. Depending on the timing of entry into the sub-study, blood samples for this study will be collected as follows:

7 days (± 1 day) 4 weeks (± 7 days) 12 weeks (± 7 days) 24 weeks (± 7 days)

Efficacy Assessments

Subjects will perform CPET using a recumbent exercise bike at Screening, on Day 1, Day 120 (\pm 30 days), Day 240 (\pm 30 days), and Day 330 (\pm 30 days). Peak oxygen consumption and peak work rate will be measured during incremental exercise testing. CPET should occur after fasting (if the subject has had a meal/ snack) for a minimum of 2 hours, with neither caffeine nor nicotine for at least 12 hours before testing.

Subjects (with or without assistive device) will perform a T1MW and T25FW at Screening, on Day 1, Day 120 (\pm 30 days), Day 240 (\pm 30 days), and Day 330 (\pm 30 days).

CPET and the T1MW/T25FW should be separated in time to allow the subject to recover sufficiently before doing the next test. All tests should be done at approximately the same time and order for each visit.

The FARS-Neuro and clinician-rated CGI scale will be performed at Screening, on Day 1, Day 120 (\pm 30 days), Day 240 (\pm 30 days), and Day 330 (\pm 30 days) by a qualified physician or health professional who is trained on the use of the tool. The CPET examination should always precede the FARS-Neuro evaluation at all visits.

A trained health professional will also work with the subject to perform the speech measurement recording at Screening, on Day 1, Day 240 (\pm 30 days), and Day 330 (\pm 30 days).

The FARS-ADL, SF-36, VAS (for Fatigue), Fatigue scale, Neuro-QoL scales (lower extremity function and upper extremity function) and Fall Questionnaire will be completed by the subjects at screening and at the visits on Day 1, Day 120 (\pm 30 days), Day 240 (\pm 30 days), and Day 330 (\pm 30 days). The Patient Global Impression of Change (PGI-C) scale and VAS (for Improvement of FA symptoms) will be completed by all subjects at Day 120 (\pm 30 days), Day 240 (\pm 30 days), and Day 330 (\pm 30 days). In between the clinic visits, subjects will also be contacted by phone by a study site staff member and asked questions relating to the PGI-C scale, Fatigue scale, Neuro-QoL scales (lower extremity function, and upper extremity function), and questions 8 and 9 of the Fall Questionnaire. These phone 'visits' will take place monthly. A Speech Assessment Questionnaire will also be completed by the subject and parents/caregiver (as applicable) at Screening, on Day 1, Day 240 (\pm 30 days), and Day 330 (\pm 30 days).

Between clinic visits subjects will be asked to keep a daily log (diary) documenting falls, near-falls, stumbles, and fear of falling.

Inclusion Criteria

To be enrolled into the study, subjects must meet the following requirements:

- 1. Male or female 12 to 50 years of age
- 2. Medical history consistent with the symptoms of FRDA at \leq 25 years of age
- 3. Detection of biallelic pathogenic variants in frataxin gene (*FXN*) (i.e. biallelic repeat expansions of GAA in the disease-causing range, or compound heterozygous for a repeat expansion of GAA in the disease-causing range + an intragenic pathogenic variant, etc.)
- 4. Ambulatory (with or without assistive device) and capable of performing other assessments/evaluations
- 5. Must be able to walk 25 feet during the timed 1-minute walk
- 6. Agree to receive calls from a diet coach regarding completion of electronic food journal
- 7. Sign the informed consent form prior to entry into the study
- 8. Agree to stay locally for the required visit days
- 9. Able to provide the necessary repeated blood samples

Exclusion Criteria	Subjects meeting one or more of the following may not enter the study: 1. Received treatment with other experimental therapies within the last 30 days prior to the first dose 2. Previously participated in the RT001 trial 3. Refusal to discontinue fish oils or other oil-based supplements for the duration of the study (Screening until last study procedure completed) 4. History of malignancies (other than basal cell carcinomas) 5. Inability to complete CPET protocol, as, for example, unable to move the pedals on the exercise bicycle, inability to maintain sufficient RPMs to finish the study, or as judged by the exercise physiologist supervising the testing
	 6. Female who is breastfeeding or has a positive pregnancy test 7. Male participant or female participant of childbearing potential, who is sexually active and unwilling/unable to use a medically acceptable and effective double barrier birth control method throughout the study
	8. Unwilling or unable to comply with the requirements of this protocol, including the presence of any condition (physical, mental, or social) that is likely to affect the subject's ability to return for visits as scheduled
	9. Clinically significant cardiac abnormalities (e.g., left ventricular ejection fraction [LVEF] < 40% on a recent echocardiogram [obtained within 12 months prior to screening] or clinically unstable arrhythmia) at screening that, in the opinion of the Investigator, would make the subject unsuitable for enrollment
	10. History of uncontrolled diabetes mellitus (Type 1 or 2)
	11. Suicidal ideation within the last 12 months as determined by the Columbia-Suicide Severity Rating Scale (C-SSRS)
	12. History, within the last 2 years, of alcohol abuse, significant mental illness, or physical opioid dependence
Food Journal requirement	While on study drug, subjects are recommended to avoid eating foods high in PUFAs. Subjects will keep food journals from screening through the completion of month 1 on study drug. After month 1, subjects will keep 2-week food journals prior to next scheduled onsite visit. Subjects (or parents/caregivers, as applicable) will have an initial call and as needed with the diet coach to discuss food journal completion requirements.
Prohibited Medications	Supplements that contain EPA or DHA are prohibited. Oil-based supplements like Fish oil, Cod Liver oil, Edible algae oil and Flax oil are also prohibited.
Statistical methods	Demographic data will be presented using descriptive statistics (e.g., mean, standard deviation, median, and range). Exposure to study drug and reasons for discontinuation will be tabulated. Safety variables will be tabulated and presented for all subjects who receive study drug or placebo capsules. Adverse events will be coded using the Medical Dictionary for Regulatory Activities (MedDRA). The incidence of treatment-emergent AEs will be presented by system organ class and preferred term. Adverse events will be presented by severity and relationship to

study drug. Changes from Baseline in clinical laboratory parameters and vital signs will be summarized across time. Shift tables will be provided for selected laboratory parameters. Physical examination results will be presented in listings.

Change from baseline (CFB) will be analyzed by comparing the change between treatment groups using a mixed model with repeated measures (MMRM). The MMRM will compare the estimated change from baseline between treatments for the primary endpoint. This analysis will assess whether there is a difference in estimated CFB between active and placebo groups at 11 months.

The primary analysis of percent change from baseline to 11 months in MVO2 as measured by CPET will use the ITT methodology and an MMRM methodology with a random slope and intercept for each individual.

All secondary and exploratory endpoints CFB values will be analyzed using the MMRM Responder analyses will be run on MVO2 (primary), GST, T1MW, Peak Workload, mFARS, and CGI-C (functional assessment). The PK of D2-LA, D2-ARA, H2-LA, and H2-ARA will be characterized in terms of minimum and maximum exposure at steady state.

For the primary analysis of peak workload, group sample sizes of 30 and 30 achieve over 99% power to reject the null hypothesis of equal means when the population mean difference is $\mu 1$ - $\mu 2 = 7.5$ - -8.3 = 15.8 with a standard deviation for both groups of 11.1 and with a significance level (alpha) of 0.05 using a two-sided two-sample equal-variance t-test.

Safety Monitoring

The blinded safety and efficacy data will be reviewed by the medical monitor on an ongoing basis. A Data Safety and Monitoring Board (DSMB) will be established to evaluate events according to the DSMB Charter. The safety and efficacy review data will not be made available to the Principal Investigators unless changes need to be made to the protocol for safety reasons.

Table 1: Schedule of Events

Assessments	Study Period	Screening		Study Drug Administration						
	Clinic Visit No.	1	2	Phone Call	3	Phone Call	4	Phone Call	5	End of Treatment Phone Call
	Study Day	Up to 30 Days	Day 1	Days 30,60, 90 (± 7 days)	Day 120 (± 30 days)	Days 150, 180, 210 (± 7 days)	Day 240 (±30 days)	Days 270, 300 (± 7 days)	Day 330 (±30 days)	4 weeks after Day 330 visit (+ 7 days)
Informed Conser	it	X								
Inclusion/Exclus	ion Criteria	X	X							
Demographics/M	ledical History	X	X							
Columbia-Suicid Rating Scale	e Severity	X								
Echocardiogram ^a	ı	X							X	
Serum Pregnancy	/ Test ^b	X								
Cardio-Pulmonai (CPET) ^c	y Exercise Test	X	X		X		X		X	
T1MW and T25I	FW .	X	X		X		X		X	
Physical Exam		X	X		X		X		X	
FARS-Neuro and CGI ^d	l clinician-rated	X^d	X^d		X		X		X	
Speech Measurer	ment Recording	X	X				X		X	
Subject complete Assessment Ques	d Speech stionnaire	X	X				X		X	
FARS ADL, SF3	6, VAS ^e	Xe	Xe		X		X		X	
Subject completed PGI-Cf, Fatigue scale, and Neuro-QoL scales		X^{f}	X ^f	X	X	Х	X	X	X	
Fall Questionnaire		X	X	Xg	X	Xg	X	Xg	X	
Vital Signs (including weight)		X^h	X		X		X		X ^h	
12-Lead ECGi		X	Xi		X		X		X	
Urine Pregnancy	Test ^{b,1}		X		X		X		X	X^{l}
Urinalysis		X							X	
Safety Laborator	y Tests ^{i,j,k}	X	Xi		X		X		X	

Protocol RT001-006: A Randomized, Double-Blind, Controlled, Phase 2/3 Study to Assess Efficacy, Long Term Safety and Tolerability of RT001 in Subjects with Friedreich's Ataxia

Lipid Profile ^{i,k}	X	Xi		X		X		X	
Randomization		X							
In-Clinic Drug Administration		X		X		X		X	
Study Drug Dispensing ^m		X		X		X		X	
Perform Drug Accountability ⁿ				X		X		X	X ⁿ
PK Sampling				X		X		X	
Biomarker Sampling		X		X		X		X	
Monitor AE/Concomitant Medication		X	X	X	X	X	X	X	Xº
Fall diary	•							-	
Food Journal	Xp	Xq		Xp		Xp		X^p	

- ^a Does not need to be performed in subjects who had echocardiogram done in the last 12 months before screening.
- b Serum and Urine Pregnancy Tests to be performed on all females, unless there is documented evidence confirming they are not of childbearing potential.
- ^c The cardio-pulmonary exercise test (CPET) should occur in the morning after fasting for a minimum of 2 hours, with neither caffeine nor nicotine for at least 12 hours before testing. All tests should be done at approximately the same time and order for each visit. The CPET should always precede the FARS-Neuro evaluation at all visits.
- d For Clinician Rated CGI, only question 1 will be answered at Screening and Day 1
- ^e Only VAS (for Fatigue) will be performed at Screening and Day 1. VAS (for Improvement of FA Symptoms) will not be performed at Screening or Day 1.
- f Patient Global Impression of Change (PGI-C) to be performed Day 30 and onwards only. Not to be performed at Screening and Day 1.
- ^g Only questions 8 and 9 of the Fall Questionnaire will be answered over phone visits
- h At Screening and Day 330, height will be collected, and body mass index (BMI) will be calculated.
- Safety labs, Lipid Profile and ECG do not have to be repeated at Day 1 if the screening and Day 1 visit is within 7 days (or less) of each other.
- ^j Safety laboratory tests include chemistry, hematology, and coagulation.
- ^k Safety laboratory tests and lipid profile should be performed in a fasting state.
- ¹ Urine Pregnancy test to be performed by subject at home on the day of the EOT phone call (before the call and after the last dose).
- ^m The study drug for the first 4 weeks of dosing will be dispensed at the study sites. Study Drug for the subsequent dosing months may be shipped to the subject or site from a drug depot or site, depending on the dispensing schedule.
- ⁿ Site to perform drug accountability with subject on the EOT call. Subject to return unused study drug/bottles to the site.
- ^o Any AE ongoing at EOT will be followed to conclusion or until stabilized.
- ^p The Diet Coach will have an initial call and as needed with the subjects (or parents/ caregivers as applicable) to discuss food journal requirement.
- ^q The food journal has to be completed through end of month 1, and every 2 weeks prior to next onsite visit.

Table 1.1: Optional PK Profile Sub-Study PK Schedule of Events

Assessments	Pharmacokinetic Profile of RT001 at Steady State in Subjects with Friedreich's Ataxia Who Participated in Study RT001-0								ly RT001-006
	Study Time	-1 Hour to - 30 Minutes (± 5 min)	30 Minutes (± 5 min)	1 Hour (± 5 min)	2 Hours (± 10 min)	4 Hours Before lunch (± 15 min)	8 Hour Before dinner (± 15 min)	12 Hour Post dinner (± 60 min)	24 Hour Day 2 (± 60 min)
	Notes	Pre- breakfast, pre-dose	Post- breakfast, post-dose	Post- breakfast, post-dose	Post- breakfast, post-dose	Pre-lunch, post-dose	Post-lunch, post-dose	Post-dinner, skip evening dose	Pre-breakfast, pre-dose
PK Sampling		X	X	X	X	X	X	X	X

[figure not shown]
Table 1.2: Optional Washout Sub-Study Schedule of Events

Assessments		Washout Blood	Levels of Subjects Who Have	Completed Treatment in RT00	01-006
	Study Day	Day 7 (± 1 day)	Week 4 (± 7 days)	Week 12 (± 7 days)	Week 24 (± 7 days)
PK Sampling		$X^{a,b}$	$X^{a,b}$	$X^{a,b}$	$X^{a,b}$

^a Draw can be performed onsite or remotely by a mobile phlebotomist

^b Subjects who complete RT001-006 are eligible to participate in any part of the PK sub-study.

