7.1. Primary endpoint

1. To demonstrate the efficacy of RT001 compared to placebo on the change of MVO2 in patients with FA through change from baseline to 11 months

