7.2. Key secondary endpoint

1. To demonstrate the efficacy of RT001 compared to placebo on an overall performance score based on a GST change from baseline to 11 months. The GST will be a combination of three endpoints (timed 1 minute walk test [T1MW], peak workload, and MVO2).

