14. STATISTICS

14.1. Statistical Plan

A complete description of analysis populations and statistical methods will be provided in a formal Statistical Analysis Plan that will be finalized prior to unblinding and statistical analysis.

Analysis populations

- All Patients Population: Any participant with any record in the database. This
 population includes both screening and randomized subjects. Population will be
 utilized for descriptive patient counts that include screening subjects.
- Intent-to-Treat (ITT) population: All participants randomized to treatment.
- Modified Intent-to-Treat (mITT) Population: All randomized subjects with at least one post-baseline efficacy evaluation will be included in the mITT population and will be analyzed as randomized. The mITT population will be analyzed for efficacy evaluations.
- Per Protocol (PP) Population: For programming purposes, they will be identified as having no major protocol violations as identified separately by the study team and the Sponsor prior to database lock. Analyses of the PP population will be analyzed as treated.
- Safety population: All participants who receive at least 1 dose of drug or placebo.

Demographic data will be presented using descriptive statistics (e.g., mean, standard deviation, median, and range). Exposure to study drug and reasons for discontinuation will be tabulated. Safety analyses will use the Safety population. Safety variables will be tabulated and presented for all subjects who receive study drug or placebo capsules. Adverse events will be coded using the Medical Dictionary for Regulatory Activities (MedDRA). The incidence of treatment-emergent AEs will be presented by system organ class and preferred term. Adverse events will be presented by severity and relationship to study drug. Changes from Baseline in clinical laboratory parameters and vital signs will be summarized across time. Shift tables will be provided for selected laboratory parameters. Physical examination results will be presented in listings.

Primary, secondary and exploratory efficacy analyses of the 11-month on-treatment period will use the mITT population and the per-protocol population unless otherwise specified.

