Change from baseline (CFB) will be analyzed by comparing the change between treatment groups using a mixed model with repeated measures (MMRM). The MMRM will compare the estimated change from baseline between treatments for the primary endpoint. This analysis will assess whether there is a difference in estimated CFB between active and placebo groups at 11 months.

The primary analysis will use the ITT methodology and an MMRM methodology with a random slope and intercept for each individual. Due to the small sample size the model will be optimized by implementation of two risk scores (baseline and slope) that account for multiple baseline covariates in one variable. The risk scores will be derived from blinded data using the GST change from baseline values and generated using the baseline model covariates (excluding treatment and visit; baseline risk score) or the baseline model covariates*time interactions (slope risk score). The risk scores will be included as covariates in the model.

To calculate the baseline risk score, the GST change score is regressed on the covariates listed below. Individual coefficients for the baseline risk score are multiplied by individual covariate values and summed. A separate slope risk score is calculated for baseline covariates interacting with time.

The MMRM with primary outcome CFB value as the response variable will include the following covariates and fixed effects:

- baseline risk score:
 - baseline score for GST
 - age
- slope risk score:
 - baseline score for GST * time
 - age*time
- Time (continuous)
- Time by treatment interaction (time*treatment)
- baseline score for parameter of interest (if not in GST)
- site pooled by region (random effect)

Model assumptions will be evaluated. If the parametric assumptions are evaluated as inappropriate or violated, rank analogues will be advanced.

All secondary and exploratory endpoints CFB values will be analyzed using the MMRM described above. This analysis will assess whether or not there is a difference in estimated CFB values between treatment group and placebo at the 11-month model estimate using least squares means estimates from the MMRM model.

Speech measurement reporting will be analyzed by a third party vendor. A separate report will be provided.

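### The primary model leaves out baseline MVO2 as its own covariate because MVO2 is a GST component; the MVO2 scale and unit also need to be stated once

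*Combined protocol and SAP*

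**What the plan says.** **Covariates.** Section 14.1 builds two risk scores by regressing GST change on baseline GST and age (baseline score) and on their interactions with time (slope score). It then lists the model terms: "The MMRM with primary outcome CFB value as the response variable will include the following covariates and fixed effects". The list holds the two risk scores, continuous time, time by treatment, pooled site as a random effect, and "baseline score for parameter of interest (if not in GST". Section 7.2 says "The GST will be a combination of three endpoints" and names T1MW, peak workload and MVO2. The condition therefore removes the direct baseline term for the primary endpoint and for both secondary endpoints.

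**Scale and unit.** The synopsis statistical methods contain the only use of percent for this endpoint: "The primary analysis of percent change from baseline to 11 months in MVO2 as measured by CPET". The paragraph just before it says "The MMRM will compare the estimated change from baseline between treatments for the primary endpoint". The objective in the synopsis and in Section 7.1 is worded as "the change of MVO2 in patients with FA through change from baseline to 11 months". CFB is expanded only as change from baseline. MVO2 is defined by name, without a unit. Section 6.4 reports the earlier study in L/min, and Section 19.1.2 calls mL/kg/min the usual expression. Section 14.3 refers to CPET without naming a parameter or scale.

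**Deferral.** Full methods are left to a "formal Statistical Analysis Plan that will be finalized prior to unblinding and statistical analysis".

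**The concern.** The measurement error in a subject's baseline MVO2 is carried, with its sign reversed, into every change value for that subject. Own baseline is the covariate that picks up this shared error. The planned risk scores reach it only in part. Baseline GST mixes MVO2 with two other tests, and the relative weights of GST and age are chosen to predict GST change, not MVO2 change. If test-retest error is a sizeable part of the variability, the primary comparison gives up precision that the collected data could supply, in a trial of only 60 subjects.

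The scale and unit wording is a smaller matter. Two statisticians working from the protocol alone could program different response variables, and an interim SD or futility result labelled only CPET could not be interpreted.

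**Working it through.** **1. The plan's own power figure.** Section 14.2 gives 30 per arm, difference 7.5 - (-8.3) = 15.8, SD 11.1 and two-sided alpha 0.05. The standard error is 11.1 × √(2/30) = 2.866 and the noncentrality is 15.8 / 2.866 = 5.51. With 58 df the power is 0.9997, which matches the stated figure of over 99%. It is for peak workload and carries no unit, so it does not inform the MVO2 model, scale or unit.

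**2. Assumed inputs for MVO2 (none is in the documents).** Baseline mean 1.2 L/min, CV 25 to 45%, and SD of 11-month change about 0.2, split two ways into true slope variation and visit error:
- First split: slope SD 0.10, visit error SD 0.1225. Variance of change = 0.0100 + 2 × 0.0150 = 0.0400. Test-retest share = 0.030 / 0.040 = 75%.
- Second split: slope SD 0.17, visit error SD 0.0745. Variance = 0.0289 + 2 × 0.00555 = 0.0400. Test-retest share = 0.0111 / 0.0400 = 28%.

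**3. Why own baseline can help.** For a single visit, the fraction of change variance explained by observed baseline is R² = σe⁴ / [(σb² + σe²) × Var(change)]. At CV 25%, σb² = 0.30² = 0.0900.
- First split: 0.0150² / (0.1050 × 0.0400) = 5.4%.
- Second split: 0.00555² / (0.0956 × 0.0400) = 0.8%.
- At CV 45% (σb² = 0.2916), these fall to 1.8% and 0.3%.

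This is the total available to observed baseline; the GST terms already capture some of it.

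**4. Cost of the term.** Counting roughly 57 subject-level residual df, one more term multiplies the standard error by about √(57/56) = 1.0089. At 80% power: 2.802 / 1.0089 = 2.777; 2.777 - 1.960 = 0.817; Φ(0.817) = 79.3%. The loss is about 0.7 points if the covariate explains nothing.

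**5. Simulated net effect.** The model had the Section 14.1 form: months 4, 8 and 11, random intercept and slope, time by treatment, and baseline-GST terms. Age and site were omitted, data were complete, and each cell had 10,000 trials. The effect was set for 80% power on absolute change at CV 35%. The table shows the change in power from adding baseline MVO2, for absolute change with constant effect and SD.

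| Split | CV 25% | CV 35% | CV 45% |
|---|---|---|---|
| First (75% test-retest) | +3.4 | +1.4 | +1.0 |
| Second (28% test-retest) | 0.0 | -0.2 | -0.2 |

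Over all cells and both scales the range was -0.8 to +4.8 points. A repeat under the same two splits gave about -1 to +3, and up to about +7 where test-retest error dominates.

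**6. Scale and unit.** A gain of 0.1 L/min is 12.5% from 0.8 L/min but 5.0% from 2.0 L/min. In the step 5 model with no treatment effect (20,000 trials per cell), each scale rejected in 5.1 to 5.8% of trials and the two disagreed in 2.2 to 4.2%. With the effect set for 80% power they disagreed in 6.5 to 25.2%. In a single-visit t-test at the standardised effect of Section 14.2 (15.8 / 11.1 = 1.42, for peak workload) they disagreed in 0 to 2%. Absolute change did better when the SD was constant. Percent change generally did better when the SD was proportional to baseline. On units: for the 40 kg adolescent of Section 6.7, an assumed 4 kg gain at unchanged L/min lowers mL/kg/min by 1 - 40/44 = 9.1%.

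**The case against.** **On the covariate.** The plan gives a reason for compressing covariates: the small sample. Leaving out a component already inside the GST avoids overlap with baseline GST. The gain is also modest, and about nil in one of the two splits. The size of the gain does have to be conceded. The overlap argument is weaker: correlation between two baseline covariates blurs their own coefficients, but under randomisation it does not blur the treatment contrast beyond the one degree of freedom in step 4. A reader might infer that the primary analysis is unadjusted for MVO2 severity, or biased. Neither follows, because baseline MVO2 contributes through the GST scores and randomisation protects the comparison.

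**On scale and unit.** A reader might infer two competing primary scales. The documents do not support that: percent change is one form of change from baseline, no section says absolute, and percent is the only scale named. The promised SAP may settle the scale, and the separate CPET manual mentioned in Section 12.2 could give the unit. What stands is that the fuller model description in Section 14.1 omits the one specific word.

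A reader might also infer a general inflation of Type I error. That is not supported. The SAP is due before unblinding, and the first optional interim releases only an SD averaged over arms and CPET-mFARS correlations. A concern arises only if the scale were still open when the second interim's futility result was known. At most one of the two interims is to be run.

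**Conclusion.** The point holds as a precision issue in the primary model. The conditional wording in Section 14.1 excludes direct adjustment for baseline MVO2, and likewise for T1MW and peak workload in their own analyses. Under assumed inputs, direct adjustment is worth between about -1 point and several points of power. It pays most when test-retest error is large relative to true variation in change and baseline spread is narrow. The documents give no MVO2 variance data, so the position within that range is unknown. The downside is bounded by one degree of freedom.

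The scale and unit matter is a wording gap to be reconciled, not a demonstrated error. It can change significance in about 2 to 4% of trials under the null, and in more with a moderate effect. The larger figures depend on an effect set for 80% power and shrink towards zero for a large effect. Confidence is high on what the text says and limited on the magnitudes.

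**What to change.** 1. In Section 14.1, remove the condition, so that the model for each endpoint includes that endpoint's own baseline directly: MVO2 in the primary model, and T1MW and peak workload in theirs. The risk scores can stay. Cost: one model term and one degree of freedom per model. The baseline tests are already scheduled.

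2. State one response scale (absolute or percent, with the sponsor's reason) and one unit for MVO2 in Section 14.1 or the pending SAP, and make the synopsis and Section 7.1 consistent with it. Weight is recorded at every site visit, so either unit can be computed.

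3. In Section 14.3, name the CPET parameter and its scale for both optional interims.

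All three should be fixed before any interim analysis. Placing them in the SAP costs a few sentences. Editing the protocol text may require an amendment and IRB approval under Section 17.8.
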